#### **4. CHANGES IN THE CONDUCT OF THE TRIAL OR PLANNED ANALYSES**

Protocol was amended during the course of the trial to increase the sample size from 250 to 300 patients (amendment 2).

Indeed, 200 evaluable patients (defined as patients who completed the trial and with a valid primary criterion) are to be secured to allow a sufficient statistical power to meet both study primary objectives. The initial sample size calculation was based on a non-evaluable patient rate (drop-out rate and non-valid primary criterion rate) of 20% (50 patients), leading to a target of 250 enrolled patients.

Based on 245 patients currently enrolled (98% of planned target), 25 patients are already dropped-out. This drop-out rate is partially due to the Covid-19 pandemic preventing 6 patients from completing the trial up to now. Furthermore, Covid-19 pandemic may continue to impact enrollment of patients and/or protocol compliance.

In addition, the current estimated number of patients with no valid primary criterion is about 68 patients.

Altogether, this current estimation of 93 (25+68) non-evaluable patients is expected to increase before the recruitment completion. As a consequence, the revised hypothesis for the non-evaluable patient rate is now about 33%.

Three additional datasets will be defined and used for secondary efficacy analyses.

Five supplemental secondary analysis of lesion visualization criteria will be conducted in addition of those described in the final Protocol Version N° 3.0 (including amendment 2) dated June 30, 2020 and the amendment for FRANCE dated June 30, 2020:

- An analysis will be performed globally. Mixed model will be considered with patient and reader as adjustment factors.
- An analysis will be performed including non-matching lesions. Mixed model will be considered by reader with patient as adjustment factor.
- Two analyses will be performed at lesion level.
  - Plain: Mixed model will be considered by reader with patient and site as adjustment factors.
  - Lesion size based: Mixed model will be considered by reader with size of lesion, patient and site as adjustment factors.
- Additional subgroup analyses will be performed considering main demographic parameters (age, sex, race, ethnicity and geographic region) and MRI machine field (1.5 tesla and 3 tesla) for the 3 co-primary criteria.

Further, the subgroup analysis by organ will include only following organs (Breast, Liver, Kidney, Pancreas, Prostate and those with more than 10% of patients for at least one reader). Patients with lesions in more than one organ will not be kept in the analysis.

In addition, if the number of patients dropping out is different between series, non-inferiority analysis will be repeated on all patients having at least one MRI performed.

Analysis of secondary criterion: patient's treatment plan will be augmented by presenting the results according to the nature (non malignant/malignant/not assessable) of the diagnosis done at unenhanced MRI and by adding therapeutic management based on unenhanced MRI

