#### 3.2. Null and alternative hypothesis

For FDA, the primary objective 1 is to be achieved for at least two readers out of three.

For EMA, both primary objectives 1 and 2 are to be achieved for at least two readers out of three.

#### Primary objective 1

The null hypothesis is that the difference in mean scores between Paired images and Pre contrast images for each of the 3 co-primary criteria is equal to 0.

*Mean (SD) of the difference between combined unenhanced and gadobutrol-enhanced imaging vs unenhanced imaging (N = 336).*

Reader	Border delineation	Internal Morphology	Degree of Contrast Enhancement
1	0.67 (0.66)	0.62 (0.47)	1.26 (0.61)
2	0.72 (0.78)	0.82 (0.61)	1.59 (0.77)
3	0.43 (0.50)	0.41 (0.52)	1.06 (0.51)

Considering that in the current trial the scale used is not exactly the same (4-point scale instead of 3-point scale for one parameter) and to account a possible greater heterogeneity, the expected difference is set to 0.35 and the expected standard deviation is set to 1.5.

Hence, expecting that for each of the 3 co-primary criteria, the difference in mean scores will be 0.35 ([“Paired” – “Pre”] within patient) with 1.5 standard deviation, a sample of 200 patients in the gadopiclenol group will have 90% power when using a single group superiority t-test with a 0.025 one-sided significance level.

As a 20% drop-out rate is expected, sample size increases to 250 patients. During the course of the study, the rate of non-valid primary criteria 1 was assessed and was eventually greater than expected (from 20% to 33%) leading to an increase of the sample size from 250 to 300 to maintain statistical power.

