#### Number of patients for the primary objective 2:

- Sample size hypothesis:

The standard deviation on lesion visualization criteria for gadopiclenol is estimated on the basis of the Guerbet Phase IIb GDX-44-004 clinical trial results on lesion visualization criteria presented in the table below.

*Mean (SD) of the combined unenhanced and gadopiclenol-enhanced imaging (N = 61).*

Reader	Border delineation	Internal Morphology	Degree of Contrast Enhancement
1	3.37 (0.55)	3.34 (0.64)	3.23 (0.80)
2	1.97 (0.74)	1.71 (0.75)	3.76 (0.58)
3	3.72 (0.49)	3.72 (0.49)	3.68 (0.50)

Considering that the results for gadobutrol would be similar (meaning that the standard deviation of the difference is expected ranging from  $\sqrt{2} * 0.50 = 0.7$  to  $\sqrt{2} * 0.80 = 1.15$ ) and taking into account a possible greater heterogeneity of patient population to be included in the study, the expected standard deviation of difference between gadopiclenol and gadobutrol is estimated to 1.75.

For this 2x2 cross-over design, the statistical analysis is based on the observed Student's t-based two-sided 95% confidence interval (95%CI) of the gadopiclenol-gadobutrol difference for each co-primary criterion. An enrollment of 200 patients is deemed necessary for the lower limit of the 95% CI to exceed the non-inferiority margin set to 0.35, assuming 80% power and for each co-primary criterion, the expected difference in mean scores is 0 with an expected standard deviation of 1.75.

If one assumed a patient drop-out rate of 20%, a minimum enrollment of 250 patients with anomalies / lesions of various body organs is planned.

Therefore, a total number of 250 patients will allow a sufficient power to meet both objectives. During the course of the study, the rate of non-valid primary criteria 1 and 2 was assessed and was eventually greater

than expected (from 20% to 33%) leading to an increase of the sample size from 250 to 300 to maintain statistical power.

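### SAP section 4 counts 93 of 245 patients as non-evaluable (38.0%) but adopts about 33% without a derivation; on its own definition 300 enrolled projects to about 186 evaluable, not 200

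*SAP*

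**What the plan says.** SAP section 4 explains the increase from 250 to 300 patients, and the protocol's rationale for global amendment 2 gives the same count. The target is that "200 evaluable patients (defined as patients who completed the trial and with a valid primary criterion) are to be secured". The status at reassessment is "Based on 245 patients currently enrolled (98% of planned target), 25 patients are already dropped-out", and "the current estimated number of patients with no valid primary criterion is about 68 patients". The sum follows: "Altogether, this current estimation of 93 (25+68) non-evaluable patients is expected to increase before the recruitment completion". The next sentence reads "As a consequence, the revised hypothesis for the non-evaluable patient rate is now about 33" per cent.

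The protocol synopsis and protocol 11.2 use 33% for both objectives and describe it as drop-outs and non-valid criteria together. SAP 3.3 (determination of sample size) words it differently. For objective 1, "the rate of non-valid primary criteria 1 was assessed and was eventually greater than expected (from 20% to 33" per cent). For objective 2, "the rate of non-valid primary criteria 1 and 2 was assessed and was eventually greater" than expected. The objective 2 calculation needs 200 patients, "assuming 80% power and for each co-primary criterion, the expected difference in mean scores is 0 with an expected standard deviation of 1.75".

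**The concern.** The only purpose of the amendment was to secure 200 evaluable patients, and the rate it adopts is presented as a consequence of the count just given. Dividing 93 by 245 gives a clearly higher rate than the one adopted, and the text expects the count to rise further. No reason is given for planning on a lower rate. The stated power for both primary objectives (90% and 80%) rests on 200 evaluable patients, so those figures depend on a number that the plan's own count does not lead to. The EMA submission needs both objectives.

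**Working it through.** **Inputs.** SAP section 4: 200 evaluable required; 245 enrolled; 25 drop-outs; about 68 without a valid criterion; 300 to be enrolled. Protocol 11.2 and SAP 3.3: difference 0.35 with SD 1.5 for objective 1; margin 0.35, true difference 0 and SD 1.75 for objective 2; one-sided 2.5% level, or equivalently a two-sided 95% CI.

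**The plan's own figures reproduce.**
- Enrolment = 200/(1 − rate). At 20%: 200/0.80 = 250. At 33%: 200/0.67 = 299. At one third: 300.
- Power from a one-sample t-test (noncentral t) at n = 200: objective 1, 90.7%; objective 2, 80.4%.

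**The rate does not.**
- Observed: (25 + 68)/245 = 93/245 = 38.0%; Wilson 95% CI 32.1% to 44.2%.
- A rate of 33% would be 0.33 × 245 = 81 non-evaluable, that is 81 − 25 = 56 without a valid criterion, not about 68.

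**Projection on the completer definition.** Evaluable so far: 245 − 93 = 152 (62.0%). Patients still to enrol: 300 − 245 = 55.

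| Assumption for the last 55 | Evaluable at 300 |
|---|---|
| 38.0% lost, as so far | 300 × 152/245 = 186 |
| 33% lost | 152 + 55 × 0.67 = 189 |
| 20% lost | 152 + 55 × 0.80 = 196 |

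Reaching 200 needs 200 − 152 = 48 of 55 evaluable (87%). The 68 is approximate. As an assumed range, 64 gives 300 × 156/245 = 191 and 72 gives 300 × 148/245 = 181. A count of 64 together with 20% loss in the last 55 gives 156 + 44 = 200.

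**By objective.** The criterion that the 68 lack is not stated, so only ranges can be given. Power is per reader and per criterion.

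*Objective 1* needs only the gadopiclenol examination (FAS1, SAP 5.2). Suppose all 68 lack criterion 1:

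| Drop-outs with a usable gadopiclenol examination | Rate | Evaluable at 300 | Power, SD 1.5 |
|---|---|---|---|
| 0 | 93/245 = 38.0% | 186 | 88.6% |
| 12 | 81/245 = 33.1% | 201 | 90.9% |
| 25 | 68/245 = 27.8% | 217 | 92.8% |

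*Objective 2* needs both examinations (SAP 2.2.1, FAS2 in SAP 5.2), so all 25 drop-outs are lost:

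| How many of the 68 lack criterion 2 | Evaluable at 300 | Power, SD 1.75 |
|---|---|---|
| All | 186 | 77.4% |
| None | 300 × 220/245 = 269 | about 90% |

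The objective 2 numbers are before PPS2 exclusions and per-reader lesion matching.

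**Sensitivity to the SD.** Protocol 11.2 derives an SD of the difference of 0.7 to 1.15 from the phase IIb data before setting 1.75. At SD 1.15, objective 2 power at n = 186 is 98.5%.

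**The case against.** The strongest reply is that 33% is a rounded planning hypothesis built on an approximate count, and that it lies inside the 95% interval for 93/245. What is expected to increase is the count of 93, not the percentage. There is also a reading that gives 33%: if 12 or 13 of the 25 drop-outs had a usable gadopiclenol examination, which is plausible with 1:1 order of injection, the objective 1 rate is 33.1% or 32.7%. All of this is fair. But compatibility with 33% is not a derivation. The plan does not state the drop-out reading, and that reading fits neither SAP section 4's definition of evaluable, which requires completion, nor objective 2, for which the same 33% is used.

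A reader might infer that the shortfall falls on objective 2, because that objective needs both examinations. The documents do not support this. Criterion 1 requires a lesion matched between pre and paired images; criterion 2 requires one matched between two sets of paired images. A patient can fail the first and meet the second. SAP 3.3 ties the higher rate to criteria 1 in one place and to criteria 1 and 2 in another. If the 68 lack criterion 1 only, objective 2 has more than enough patients.

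SAP 3.3 might also be read as using a second, conflicting definition, since it mentions only non-valid criteria. For objective 2 this is weak: a drop-out without both examinations has no valid criterion 2, so the two descriptions can cover the same patients.

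**Conclusion.** The mismatch stands: the plan's own count gives 38.0%, and the adopted 33% is neither that figure nor derived from it. On the completer definition, 300 enrolled projects to about 186 evaluable if the observed rate continues, or 189 if 33% applies to the last 55. Confidence in the mismatch is high. Confidence in any projection for a single objective is only moderate, because it depends on the undisclosed basis of the 68 and on how many drop-outs have a usable gadopiclenol examination.

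It might be inferred that the trial is underpowered or that 300 is too few. That does not follow. In the lowest case worked for objective 2 at the observed count, 186 patients, per-test power is 3 points below its value at 200, and only at an SD set well above the source-based range; at SD 1.15 it is 98.5%. Severity is minor.

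**What to change.** Do not enrol more patients. In the protocol synopsis, protocol 11.2, SAP 3.3 and SAP 4:

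(a) State which primary criterion the 68 patients lack, and on what reader basis (any reader, all readers, or each reader).

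(b) Replace 33% with the observed rate (93/245, about 38%), or give the derivation of 33%, including the rate assumed for the last 55 patients.

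(c) Keep 300 as the enrolled number. Replace the statement that 200 evaluable patients are to be secured with the expected evaluable number for each objective, computed from the counts in (a) and from the number of drop-outs with a usable gadopiclenol examination. No per-objective figure should be printed before (a) is answered.

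(d) Restate per-test power at those numbers. If the completer figure of 186 turns out to apply, that is about 77% for objective 2 at SD 1.75 and about 89% for objective 1 at SD 1.5.

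The cost is wording in four places and two counts: the 68 by criterion and reader, and the drop-outs with a usable gadopiclenol examination. The stated power may fall by up to about 3 points. Tests, margin, analysis sets and decision rule are unchanged.

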## 5. STATISTICAL AND ANALYTICAL PLANS

### 5.1. Disposition of patients

Number of patients attending each visit will be presented by series (gadopiclenol-gadobutrol / gadobutrol-gadopiclenol) and overall.

The patients' disposition will be presented by series and overall. The reason of screen failure for not randomized patients will be presented overall and the reason of premature discontinuation for randomized patients will be presented by series and overall. The same analyses will be repeated by body regions except reason of screen failure.

If a patient withdrew for Adverse Event and at least one adverse event is coded with PT=« COVID-19 » then the reason of premature withdrawal will be put at COVID-19 but if no AE is coded with PT=« COVID-19 » then the reason of premature withdrawal will be put at Adverse Event other than COVID-19

If a patient withdrew for other reason, then the reason of premature withdrawal will be derived from the specify field as the following:

Specify field	Reason of premature withdrawal
“COVID-19 crisis preventing patient to follow protocol schedule”	COVID-19 crisis preventing patient to follow protocol schedule
“Withdrawal of patient’s consent due to Covid-19 crisis”	Withdrawal of patient’s consent due to Covid-19 crisis
Other	Other reason

Number of patients by country and center will be presented overall as well.

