 - Other AE-targeted action: therapeutic measures other than corrective drug administration (e.g. ice, heating pad, brace, cast...) or patient underwent a procedure (surgery, physiotherapy, additional laboratory test...) for this AE. The therapeutic measure(s) should be reported in the appropriate section of the clinical eCRF ("Procedures / therapeutic measures" section).

 CONFIDENTIAL	Protocol No. GDX-44-011 Version No. 3.0 (including amendment 2) June 30, 2020	Page 56 / 82
---	---	--------------

- Trial discontinuation: the AE leads to a patient discontinuation from the trial.
- **Adverse event of special interest (AESI):** see [section 9.3.3](#) for AESI definition.
- **Assessment of the seriousness of the AE:** see [Section 9.2](#) for SAE definition.

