10.4 Reasons for patient's screening failure and premature discontinuation

Criteria for screen failure and premature discontinuation of patients:

- Inclusion criteria not met /Non-inclusion criteria met;
- Adverse Event (according to the investigator's judgement);
- Adverse Event of Special Interest (AESI)
- Withdrawal of patient's consent:
 - o If the patient withdraws consent for disclosure of future information, Guerbet may retain and continue to use any data collected before such a withdrawal of consent.
 - o If a patient withdraws from the trial, he/she may request destruction of any samples taken and not tested, and the investigator must document this in the site's records.
- Patient lost to follow-up (date of last contact will be documented in the medical file and the clinical eCRF). Any effort will be undertaken to know the reason for this loss to follow-up and/or to exclude any adverse reaction as this reason. This will be documented in the patient's medical file;
- Discovery of an unexpected, significant, or unacceptable risk to a patient enrolled in the trial;
- At the discretion of the investigator if the patient safety or well-being is not compatible with trial continuation;
- Other reason (to be specified).

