### Overall Safety Summary

An overall summary of NTEAEs will be presented using the SPS. The table will be presented with the overall “Total” column only.

The total number of events and number of patients with at least one event was tabulated for the following events :

- All AEs.
- Serious AEs (SAEs) (variable “serious” classified as yes or missing) - patients with AEs having different seriousness criteria will be counted in each category of seriousness criterion.
- AEs of special interest (AESIs) (preferred term is Nephrogenic systemic fibrosis).
- AEs with causal relationship to a trial procedure.
- AEs according to intensity (patients with AEs having different intensities will be counted in each category of intensity).
- AEs according to the outcome (patients with AEs having different outcomes will be counted in each category of outcome).
- AEs requiring a concomitant drug (AE-targeted medication).
- AEs requiring a concomitant procedure/therapeutic measures (other AE-targeted action).
- AEs leading to trial discontinuation.

Furthermore the distribution of the number of AEs reported by patient (0, 1, 2 or 3 or more AEs) will be also presented.

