### TEAEs

The same table will be displayed by contrast agent groups and periods for Treatment Emergent AEs (TEAEs). The terms “NTEAE” will be replaced by “TEAE”. The following variables will be presented in addition:

- TEAEs with causal relationship to the IMP.
- TEAEs leading to discontinuation of the IMP.
- TEAE leading to IMP unblinding

Same analyses will be repeated by body regions.

The number and percentage of patients with at least one TEAE and the number of TEAE will be presented by contrast agent groups and period and overall according to Primary SOC and PT.

The table will be sorted by descending frequency of SOC and, within each SOC by descending frequency of PT according to the Total column.

Same analyses will be repeated by body regions.

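### SAP 5.1 labels any adverse-event withdrawal as COVID-19 if the patient has any AE coded COVID-19, without requiring that AE to be the one that led to withdrawal

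*SAP*

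**What the plan says.** For patients whose recorded reason is an adverse event, SAP 5.1 uses a two-branch rule.

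- The first branch opens with this condition: "If a patient withdrew for Adverse Event and at least one adverse event is coded with PT". The preferred term named is the one for COVID-19, and a patient who meets the condition is reported as a COVID-19 withdrawal.
- The second branch covers patients none of whose AEs carries that term: "then the reason of premature withdrawal will be put at Adverse Event other than COVID-19".

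The section also says that the "reason of premature discontinuation for randomized patients will be presented by series and overall", and that these analyses are repeated by body region. The outputs are Tables 14.1.1.4 and 14.1.1.5.

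Two protocol provisions bear on the rule. Section 10.4 lists as a reason "Adverse Event (according to the investigator's judgement"), so the site decides that an AE was the cause. Section 9.1.3 provides, for each AE, an entry under other action taken: "Trial discontinuation: the AE leads to a patient discontinuation from the trial".

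The SAP's Overall Safety Summary separately counts "AEs leading to trial discontinuation". Its TEAEs section adds: "The same table will be displayed by contrast agent groups and periods for Treatment Emergent AEs (TEAEs").

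**The concern.** The rule replaces cause with co-occurrence. It asks whether a COVID-19 event appears anywhere among the patient's AEs, not whether that event ended participation. It sets no order in time either, so a COVID-19 AE recorded after the patient had stopped would also trigger the label. That can happen, because Protocol 14.3.2 asks the investigator to go on collecting safety information after discontinuation.

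The rest of the plan handles pandemic effects by cause. In the same section, withdrawals for other reasons are classified from what the site wrote in the specify field. In SAP 5.2, deviations are set apart only when their reason is related to the pandemic.

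At stake is a descriptive result. In a two-period crossover, a patient who stops after the first injection because of an AE tells the reader something about the tolerability of that agent. Placing such a patient in a row that reads as an external cause understates the row a reader would consult for that purpose.

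**Working it through.** The plan gives no figure to reproduce, so the check applies the literal rule to each possible case.

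**Inputs.** The rule and its complement come from SAP 5.1. The AE-level action *Trial discontinuation* comes from Protocol 9.1.3. The complement applies only when no AE is coded COVID-19, which confirms that the rule searches all of the patient's AEs.

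| Case | AE that led to withdrawal | Other AEs recorded | Label under SAP 5.1 | Label if tied to the AE that led to withdrawal |
|---|---|---|---|---|
| 1 | COVID-19 | none | COVID-19 | COVID-19 |
| 2 | not COVID-19 | no COVID-19 AE | other than COVID-19 | other than COVID-19 |
| 3 | not COVID-19 | unrelated COVID-19 AE | **COVID-19** | **other than COVID-19** |
| 4 | COVID-19 | unrelated other AE | COVID-19 | COVID-19 |

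Only case 3 is misclassified, and tying the rule to the AE that led to withdrawal corrects it without changing the other three.

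**Effect on the table rows.** Let A be all patients withdrawn for an AE, C those in cases 1 and 4, and k those in case 3.

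- Under SAP 5.1, the COVID-19 row is C + k and the other-than-COVID-19 row is A − C − k.
- With the correct link, the rows are C and A − C.
- The error is +k in one row and −k in the other. The sum is (C + k) + (A − C − k) = A either way.

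The sum is preserved because only AE withdrawals feed the COVID-19 row. Withdrawals because the pandemic prevented the schedule from being followed, or because consent was withdrawn on account of it, come from the other-reason specify field and have their own labels in SAP 5.1.

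**Other places where the event is counted.** The treatment-emergent overview counts AEs leading to trial discontinuation by agent and period. That count does not pass through the 5.1 derivation, so k does not enter it.

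**Size of k.** No document gives it. Case 3 needs both a COVID-19 AE and a different AE that caused withdrawal. Planned participation lasts at most 23 days (Protocol 3.3.1), and Protocol Table 4 stops collection of unrelated AEs once participation ends. The window is therefore short, although the SAP's deviation list implies a later last contact for patients in France, 7 to 14 days after the last injection.

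**The case against.** The strongest reply is that little depends on this label, and most of that reply stands. Both derived rows subdivide one recorded reason, so a reader who adds them recovers the correct number of AE withdrawals. Contrast reactions also stay visible by agent in the treatment-emergent overview, in the tables of IMP-related events and in the AE listings. What the reply does not answer is that the split between the two rows is itself reported, by series and body region, and in case 3 it is wrong.

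A reader might draw four stronger conclusions, which the documents do not support.

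- *Product-related withdrawals disappear from the report.* They do not; they move between two AE rows, and the safety tables still count them.
- *The disposition and safety tables will contradict each other.* The safety row is not split by COVID-19, so it should be compared with the sum of the two disposition rows, which the error leaves alone. A gap against the other-than-COVID-19 row by itself would arise for correctly labelled COVID-19 withdrawals too.
- *The missing-data position in SAP 3.1 is weakened.* That passage contrasts drop-out caused by first-period diagnostic results with drop-out for safety or technical reasons. Neither COVID-19 nor another AE is a diagnosis-driven reason. The drop-out analysis in SAP 5.6.2 depends on the number of drop-outs per series, not on their reasons.
- *The pandemic drop-outs show the rule at work.* SAP section 4 reports 25 drop-outs among 245 enrolled and says the pandemic prevented 6 patients from completing. That description fits the separate schedule-related label and says nothing about patients with a COVID-19 AE.

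**Conclusion.** The point holds as a minor defect in a pre-specified derivation. Read literally, SAP 5.1 misclassifies an AE withdrawal whenever the AE that led to it is not COVID-19 but an unrelated COVID-19 AE is also on record. The error equals the number of such patients, is confined to the two AE rows of Tables 14.1.1.4 and 14.1.1.5, and always runs toward understating adverse events other than COVID-19. The number is not given and may be zero. Total AE withdrawals, agent-level safety counts and all efficacy conclusions are unaffected.

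This rests on two assumptions: that the rule is programmed as written, and that the action field in Protocol 9.1.3 is completed for the AE that led to withdrawal. It is worth correcting because the rule is plainly not what a reader of the table would assume, and the variable needed is already collected.

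**What to change.** Replace the adverse-event rule in SAP 5.1 with wording to this effect:

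> For a patient withdrawn for an adverse event, the reason is COVID-19 only if the AE with other action taken = Trial discontinuation is coded PT COVID-19; otherwise it is Adverse Event other than COVID-19. If both a COVID-19 and a non-COVID-19 AE carry that action, the single reason is Adverse Event other than COVID-19 and the patient is listed. If no AE carries that action, the site is queried before database lock.

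The second sentence keeps the reasons mutually exclusive, so the rows still add up to the number of discontinued patients. Counting such a patient in both rows would lose that. The third sentence prevents a blank action field from deciding the label by default.

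The cost is the SAP sentence, a small amount of programming and possibly a few site queries. No new data item is needed.
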